Research Protocol: 18F-DOPA PET to Elucidate the Antidepressant Mechanism of Lurasidone in Bipolar Disorder

9/17/2019

Recruitment Procedures

Patients will be recruited through referrals from treating outpatient psychiatrists, or from clinics at Columbia University. Advertisements will be placed through the Columbia University website including the "RecruitMe" site and on advertising sites such as Craig's List. A website that describes the study will be created. Messages will be posted on email list-serves of mental health clinicians describing the study and asking for referrals. Subjects will be recruited by Depression Evaluation Service members through IRB#6669R.

Study staff and investigators will contact subjects who respond to advertising efforts to screen and recruit eligible individuals. For clinical patients at Columbia, only subjects who the clinical staff has identified as appropriate will be approached. The clinical staff will first ask the patient if he or she can be approached by research staff. Only if the subject agrees to be approached will the staff from this study do so. All potential subjects will be given the telephone number of the research coordinators who will discuss the purpose and procedures of the research and screen the subjects for potential eligibility.

Texts of written materials to be distributed via advertisements and websites will be submitted to the IRB for approval before they are distributed.

1. Initial screening will be completed as detailed in IRB#6879R or IRB#6669R.

2. If eligible, subjects will be asked to sign the consent form for IRB# 4815 ([name]). Participants will then be given a physical exam, laboratory test (via blood draw) and psychiatric examinations as performed under IRB#4815. IRB#4815 allows for clinical assessments, a medical screening for significant illness, a screening for drugs of abuse, a developmental history and acquisition of blood samples for genetic analyses. IRB#4815 allows for the above procedures so that subjects can enter any of several different types of studies and protocols.

3. If eligible for IRB#4815, subjects will be given a detailed verbal explanation of this study by a research psychiatrist. During the consent process, the consenting psychiatrist will obtain a history of participants' past radiation exposure. Participants will then give written informed consent if they choose to participate in the study.

Inclusion Criteria

Criterion	Method of Assessment

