PET Imaging: Each subject will undergo two PET scans with [18F]DOPA at the David A. Gardner PET Center at [name]. One scan will be before lurasidone is initiated and the second will be four weeks (+/- one week) after starting lurasidone. Patients will not eat within 12 hours of the PET scan with the exception of a low-protein meal more than four hours before the scan. A urine pregnancy test will be done on females on the day of each PET scan, before the scan, to assure that pregnancy has not occurred between the time of laboratory tests at screening, during which a serum pregnancy test is conducted, and the PET scan. Patients will be given 150 mg of carbidopa PO within 120 minutes of the radiotracer injection. Carbidopa is used to prevent AAAD decarboxylation of the radiotracer so that it is bioavailable to cross into the brain. The subject will have an intravenous line placed for radiotracer injection. An arterial line will be placed in the radial artery of the other arm by an experienced physician, [name]. [name] will be present during the scan until the arterial line is removed. An MD clinician from the MIND Division will be on the CUMC campus and avilable during the scan via telephone. If [name] is not available, [name] or [name] will be present during the scan until the arterial line removed. Patients will have vital signs measured before radiotracer injection and after PET scan is complete. If there is an complication with the arterial line placement, including patient refusal at the time of scan, the scan will proceed without blood sampling.

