Clinical Treatment: Open-label lurasidone will be taken by participants after a meal, beginning at 20 mg daily for the first two weeks. At that time, the dose can be increased to 40 mg daily for two weeks. Dosage will be raised only if the participant is tolerating the medication and has not been rated "much improved" or "very much improved" on the CGI improvement scale for that week. At week 4, blood samples will be drawn to measure blood glucose and lipids for safety monitoring. Treatment will be up to 4 weeks or until the second PET scan. Study visits will be weekly with a MIND or DES psychiatrist, unless the participant is rated much improved at week four, in which case visits will be biweekly thereafter. Additional visits can be scheduled at the study doctor's discretion for purposes of clinical management. At each visit, the study psychiatrist will complete the MADRS, YMRS, CGI, CSSRS, psychotic symptoms of BPRS, and SAFETEE-GI. Patients will complete self-rating forms at each visit. Participants with a Clinical Global Improvement (CGI) score of 6 ("much worse") or 7 ("very much worse") on two consecutive weeks during the trial will be terminated early from the study. Patients without alcohol or benzodiazepine use disorder may receive benzodiazepines for insomnia or anxiety/agitation (maximum dose equivalent to 4 mg of lorazepam per day). All patients may also receive zolpidem or diphenhydramine for insomnia or agitation.

Lurasidone and all laboratory tests will be provided for free of charge to the participant. Participants will receive six months of free outpatient treatment including the treatment obtained through this protocol, with treatment visits at least monthly.

Emergency Procedures: A research psychiatrist will be available by cell phone at all times during the study. Patients requiring urgent admission at the time of a study visit will be brought to the CUMC Emergency Department by the study physician and if necessary, security assistance will be provided. The treating psychiatrist will arrange non-urgent hospital admissions, preferably to the NYSPI 5-South unit. If patients refuse hospitalization but the clinical team determines that this is needed, the team will arrange all necessary interventions including contacting the local crisis team, family or Emergency Medical Services.

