Patients lost to follow-up: Upon enrollment, patients will be asked to provide the name and phone number of at least two persons who will likely know their future whereabouts. These people will be contacted if the subject is lost to follow up.

Criteria for Early Discontinuation

1) Intolerable side effects of lurasidone

2) Refusal to continue regimen and willingness to receive open treatment 3) DSM-IV criteria for a manic episode or score > 12 on the YMRS

4) During the washout period, if subjects score a six (much worse) or seven (very much worse) on the CGI- I, the protocol will be discontinued. If the participants do not tolerate the washout because of marked agitation, severe anorexia such as inability to drink adequate amount of fluids, or suicidal ideation or behavior with plan or intent, the protocol will be discontinued. In these cases, subjects will be offered open clinical treatment.

5) During the lurasidone treatment phase, if subjects score a six (much worse) or seven (very much worse) on the CGI-I for two consecutive weeks, the trial will be terminated early. If there is clinical reason to change to open treatment, such as onset of psychotic symptoms, manic symptoms of clinical concern, active suicidal ideation on two consecutive visits, the clinical team will evaluate whether the risks outweigh the benefits of continuing protocol.

6) If the patient requests withdrawal for any reason.

7) The PI judges that it is medically unwise to continue in the study, for example if the subjects are unable to comply with the study procedures and rules.

Radiotracer Information

Name of the radiolabeled drug/compound: [18F]DOPA

Manufacturer and other information: [18F]DOPA will be synthesized by the David Gardner PET Center at CUMC. IND 140398 is to use [18F]DOPA with lurasidone (latuda) as per this PSF. Lurasidone (Latuda) will not be used in an off label manner, however.

IND is approved IND# 140398. IND is held by PI/CU Investigator [name], MD

Data Analysis Plan

The aim of the analyses is to provide feasibility data for a larger grant application. We will visualize all data to assess for trends that are not detectable in standard statistical analyses due to the small power of this preliminary study.

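### Should the plots be marked by lurasidone dose at scan 2, given that dose depends on early response?

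*Combined protocol and SAP*

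**What the plan says.** The Clinical Treatment section starts everyone on open-label lurasidone 20 mg daily for two weeks. It then says: "At that time, the dose can be increased to 40 mg daily for two weeks". The step is permitted, not required, and it is conditional: "Dosage will be raised only if the participant is tolerating the medication and has not been rated" in the top two CGI improvement categories that week. On duration the same section says: "Treatment will be up to 4 weeks or until the second PET scan".

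Under PET Imaging, the first scan precedes lurasidone and "the second will be four weeks (+/- one week) after starting lurasidone". The first item under Criteria for Early Discontinuation is "Intolerable side effects of lurasidone".

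The Data Analysis Plan has two sentences. One gives the aim, which is feasibility data for a larger grant application. The other says "We will visualize all data to assess for trends" that standard analyses would miss "due to the small power of this preliminary study". It names no dose variable, covariate, stratum or particular plot. The mechanism aim appears in the title: "18F-DOPA PET to Elucidate the Antidepressant Mechanism of Lurasidone".

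**The concern.** Dose at scan 2 is partly an outcome. The 40 mg group consists of patients who tolerate the drug and had not clearly improved by week 2. The 20 mg group mixes early responders, patients with milder intolerance, and anyone left at 20 mg by discretion. Patients with intolerable effects leave the study.

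Given the title, the natural display is PET change against clinical improvement. Dose is tied to improvement by the titration rule. If dose also shifts [18F]DOPA uptake, it becomes a common factor behind both axes. Points drawn without a dose mark could then show a trend that comes from titration, or hide a real one. Trends are to be judged by eye, and one could be carried into the grant application as evidence of mechanism. Marking each point by dose looks like a safeguard that costs almost nothing.

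**Working it through.** **What the documents supply.** They give the two doses, the week-2 rule and the scan window. They give no sample size, response rate, PET variance or dose effect on PET, so there is no planned figure to reproduce. All inputs below are assumptions.

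**Model.** Z4 is standardised improvement at week 4. Week-2 improvement correlates rho with it. A patient is raised if week-2 improvement falls below the cut that leaves a fraction q not yet much improved, if the drug is tolerated (probability t), and if the clinician uses the option (probability c). PET change is r·Z4 plus noise, scaled to unit variance, plus d for those raised. There is no clinical gain from 40 mg unless stated. With φ the normal density and x_q the q-quantile:

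- share at 40 mg: p = q·c·t
- covariance of being raised with Z4: k = −rho·c·t·φ(x_q)
- correlation in the unmarked plot: (r + d·k) / √(1 + d²·p(1−p) + 2·d·r·k)

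**Ranges.** q 0.4 to 0.8, rho 0.7 to 0.9, c 0.5 to 1, t 0.9 to 1. Then p runs from 0.4 × 0.5 × 0.9 = 0.18 to 0.8 × 1 × 1 = 0.80.

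**No true relation (r = 0), all scanned patients tolerating (t = 1), d = +0.5 SD.**

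- Largest: q 0.6, rho 0.9, c 1. φ = 0.386, k = −0.348, p = 0.6. Correlation = −0.174/√1.06 = −0.17.
- Smallest: q 0.8, rho 0.7, c 0.5. φ = 0.280, k = −0.098, p = 0.4. Correlation = −0.049/√1.06 = −0.05.
- At d = +1 SD the same two cells give −0.348/√1.24 = −0.31 and −0.098/√1.24 = −0.09.
- A negative d reverses the signs. At d = 0 the correlation is exactly 0.
- If 40 mg also brings a 0.5 SD clinical gain, simulation gives −0.13 to +0.01 for d = +0.5, so even the sign is not fixed.

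**True r = 0.30** (q 0.6, rho 0.8, c 1, t 0.9; k = −0.278, p = 0.54).

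- d = +0.5: (0.30 − 0.139)/√(1 + 0.062 − 0.083) = 0.161/0.989 = 0.16.
- d = −0.5: (0.30 + 0.139)/√(1 + 0.062 + 0.083) = 0.439/1.070 = 0.41.

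**Sampling error.** The 95% half-width around r = 0 is tanh(1.96/√(N−3)): 0.63 at N = 10, 0.44 at 20, 0.36 at 30. The largest false correlation above, 0.31, is below the smallest of these.

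**Cost of splitting by dose.** With d = 0 the unmarked plot shows the true 0.30. Conditioning on dose restricts the range of improvement, because dose was assigned on early improvement. In the same setting, simulation gives:

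| | 20 mg group | 40 mg group | Pooled, dose-adjusted |
|---|---|---|---|
| All eligible raised (c = 1) | 0.26 | 0.24 | 0.25 |
| Half raised (c = 0.5) | 0.30 | 0.24 | 0.29 |

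At an assumed N of 20, 18% to 80% raised is about 4 to 16 patients at 40 mg, so the smaller group may have only 4. For a group of 4 the half-width is tanh(1.96/√1) = 0.96.

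**The case for a change.** The strongest reply is that the distortion is a bias. A larger sample does not remove it, and a wide interval in the pilot does not make it harmless when trends are read by eye and passed to a grant application. The titration rule certainly links dose to early response, and the plan is silent on dose. One sentence would settle it with no extra patients or visits. All of that is factually right, and marking points by dose is a sensible habit.

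Three things limit its force. First, the bias needs an effect of 40 versus 20 mg on [18F]DOPA uptake, for which the documents offer no support. Second, a reading of the plan's all-inclusive wording broad enough to cover a plot of PET change against improvement is broad enough to cover dose, which is equally study data; the text settles neither. Third, only the marking is nearly free. Describing trends within dose groups, or adjusting for dose, conditions on a consequence of early response and can weaken a real signal, as the table shows. Recording days at dose and the reason for staying at 20 mg would add data items, and the documents do not describe how dose is recorded.

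The scan window raises a separate scheduling question. A raise at day 14 leaves 7, 14 or 21 days at 40 mg for scans at weeks 3, 4 and 5. The last fits poorly with the two-week period at that dose and with the treatment duration under Clinical Treatment. Those passages and PET Imaging must be reconciled, but this has no bearing on how plots are labelled.

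**Conclusion.** No change to the analysis plan is called for. The observation is correct: scan-2 dose follows partly from early CGI response and tolerability, and the Data Analysis Plan does not name dose. It is missing detail in a feasibility-only plan that commits to no plot, test or mechanism claim and already admits low power. Dose is known to everyone in an open-label study, so analysts can label points by it in the ordinary course, and no stated result depends on the omission.

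Under assumed inputs, with no true relation and no clinical gain from 40 mg, the false correlation is about 0.05 to 0.17 in size for a 0.5 SD dose effect and 0.09 to 0.31 for 1 SD, with all scanned patients tolerating. It is zero if dose does not affect uptake. All of this lies within the 0.36 to 0.63 half-width at an assumed 10 to 30 patients. A requirement to read trends within dose groups would be a debatable trade rather than a clear gain: a true 0.30 becomes about 0.24 to 0.30, in groups that may number as few as 4. These figures illustrate the mechanism; they are not estimates for this trial.

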`Medication Washout: If patients are eligible to participate in the study, and they are taking psychiatric medications at the time of recruitment, they will have the psychiatric medications tapered off. The patients will be off of all medications for three weeks before PET scanning. This medication-free treatment period is necessary to obtain imaging and clinical outcome data that are not significantly influenced by previous medications. The design will also allow us to measure the clinical response to lurasidone that is independent from an interaction with the previous medications. Patients will meet with a psychiatrist from MIND or DES at least weekly

in person during this time. A CGI, HAM-D, YMRS, psychotic symptoms of BPRS and CSSRS will be performed at least weekly to detect new onset of manic symptoms or clinical deterioration. Only patients who still meet inclusion criterion of HAM-D>15, including atypical depression items addendum, at the clinical appointment one week before the scheduled PET scan will continue.

Patients who no longer meet inclusion criteria at the end of the period, including those that are no longer sufficiently depressed, will not continue with imaging and will be offered up to 6 months of open label outpatient treatment.

Frequency of Clinical Visits: Throughout the study, outpatients will meet with a treating MIND or DES psychiatrist at least once a week in-person. Subjects will do the washout on the 4 Center or 5 South unit if clinically warranted. Inpatients will be evaluated by their physician at least three times weekly. In addition, all inpatients are monitored at intervals on an around-the-clock basis by ward clinical staff. During the washout period, inpatients will generally see a psychiatrist daily, except for weekends and holidays.

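### Does a second PET scan after day 28 leave lurasidone exposure so unclear that the comparison of the two scans suffers?

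*Combined protocol and SAP*

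**What the plan says.** Under Research Procedures, the PET Imaging section schedules one scan before lurasidone and says that "the second will be four weeks (+/- one week) after starting lurasidone". The Clinical Treatment section starts everyone on 20 mg daily for two weeks and continues: "At that time, the dose can be increased to 40 mg daily for two weeks". The increase is conditional: "Dosage will be raised only if the participant is tolerating the medication and has not been rated" as much or very much improved on the CGI. The same section sets the length of treatment: "Treatment will be up to 4 weeks or until the second PET scan". Visits are weekly, but participants much improved at week four move to a lighter schedule, "in which case visits will be biweekly thereafter". Six months of free outpatient care is also promised, with the protocol treatment counted within it.

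For the first scan, the Medication Washout section states the drug condition: "The patients will be off of all medications for three weeks before PET scanning", described as "necessary to obtain imaging and clinical outcome data that are not significantly influenced by previous medications". The Data Analysis Plan is two sentences long. It opens with "The aim of the analyses is to provide feasibility data for a larger grant application" and then says that all data will be visualized because power is small.

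**The concern.** The scan window runs a week beyond the 28 days that the dose steps add up to, and the sentence on treatment length does not say whether the earlier or the later limit applies. For a late scan, two clinicians could follow the text and leave their participants in different drug states. One reading carries the 40 mg step past two weeks. The other leaves a gap of up to a week without protocol lurasidone. The drug state at the first scan is spelled out, and no matching statement exists for the second.

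The design exists to compare the two scans. If some second scans were done after the drug had been stopped, and its effect on [18F]DOPA uptake faded in that time, the mean change would be too small. Recruiting more participants would not cure that, and the diluted figure could pass into the planning of the larger study. A second strand is that dose at the second scan depends on early response and tolerability, so a comparison of participants on 20 mg and 40 mg would be confounded by response.

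**Working it through.** **Inputs.** Scan window: 28 ± 7 days (PET Imaging). Dose steps: 14 days at 20 mg, then optionally 14 days at 40 mg (Clinical Treatment).

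**The plan's own figure.** 14 + 14 = 28 days, which agrees with the stated four weeks.

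**Days affected.** The window is 28 − 7 = 21 to 28 + 7 = 35, which is 15 days. The limits differ only on days 29 to 35: 7 of 15, or 47% of the calendar window. On days 21 to 28 both readings give the same exposure.

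**Exposure for a scan on day *t*, counting from a start at day 0.** Treated to the scan, a raised participant has *t* − 14 days at 40 mg. Stopped at four weeks, the same participant has 14 days at 40 mg and *t* − 28 days without protocol drug.

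| Scan day | Treated to scan: days at 40 mg | Stopped at 4 weeks: days at 40 mg | Days without protocol drug |
|---|---|---|---|
| 28 | 14 | 14 | 0 |
| 29 | 15 | 14 | 1 |
| 35 | 21 | 14 | 7 |

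If the first dose is day 1 and the scan-day dose is not counted, the day-35 maxima become 20 and 6.

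Cumulative dose at day 35:

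- Raised, treated to scan: 14 × 20 + 21 × 40 = 1,120 mg. Stopped at four weeks: 14 × 20 + 14 × 40 = 840 mg.
- Never raised, treated to scan: 35 × 20 = 700 mg. Stopped at four weeks: 28 × 20 = 560 mg.

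The full spread across participants is wider, from 21 × 20 = 420 mg to 1,120 mg. Much of that comes from the openly stated window and the optional increase, not from the unclear sentence.

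**Dilution.** Let *q* be the share of second scans done off drug, *L* the share of the effect lost in them, and *d* the full effect in SD of the change. The mean change is *d*(1 − *qL*), so the bias is *dqL*. The documents give none of these inputs, nor N; all values below are assumptions.

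- Treated to the scan (*q* = 0), or no fading (*L* = 0): bias 0.
- *q* = 0.25, *L* = 0.5, *d* = 0.5: bias 0.5 × 0.125 = 0.06 SD.
- *q* = 0.47, *L* = 1: bias 0.23 SD at *d* = 0.5, or 0.47 SD at *d* = 1.

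For comparison, the standard error of the mean change is 1/√N: 0.32 SD at N = 10 and 0.22 SD at N = 20. The middle case is well inside one standard error. The extreme case is about one standard error or less at *d* = 0.5, and 1.5 to 2.1 at *d* = 1. That extreme requires scans spread evenly over the window, the four-week stop applied to every late scan, and the whole effect gone even one day after stopping.

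**Reading the sections together.** The sentence on treatment length joins its two limits with *or*. Treating up to a day-35 scan meets the second limit, so the sentence is not contradicted. The second scan is timed from the start of lurasidone, and visits are foreseen beyond week four. No section says that lurasidone stops before the scan. The two-week length of the 40 mg step fits a scan at the nominal four weeks and is silent on the tolerance around it.

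**The case for a change.** The strongest opposing case is that the text does not settle the matter. No section requires participants to be on lurasidone at the second scan. Later visits and the six months of care do not name a drug or dose, so they are only indirect support for continuity. If treatment does run to a late scan, the two-week length of the 40 mg step no longer fits. A small study read from individual plots has particular need to know each participant's exposure, because one unmarked point scanned a week off drug could mislead the eye. Writing the rule down would also cost very little.

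What stands is that the wording is incomplete for days 29 to 35. What does not stand is the step from there to a damaged result. The off-drug case has to be inferred, and its dilution rests wholly on assumed inputs. The contrast with the first scan is also less clean than it looks, since the Inclusion Criteria allow benzodiazepines and hypnotics throughout the study despite the washout wording.

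The link between dose and response is real, but no comparison by dose is planned. CGI and side-effect ratings, on which the increase turns, are already collected at every visit.

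**Conclusion.** The day counts are right and the gap is real: for 7 of the 15 permitted scan days, neither the end of treatment nor the length of the 40 mg step is stated. It is missing detail in an open-label pilot, not a contradiction. The study team schedules the scan and sets the dose at regular visits, and would be expected to resolve the point in practice. How to reconcile the two sections for late scans is a clinical decision for that team, and nothing here favours one answer on clinical grounds.

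Statistically, the bias is zero if participants are treated up to the scan, which is the more natural reading of the text. It can be appreciable only under several unfavourable assumptions together, none of which the documents support with a figure. The analysis plan offers feasibility data and plots and has no estimate, test or sizing rule. Stating the limit more fully would therefore change no planned analysis or conclusion. The judgement rests on that reading of the treatment sentence and on the descriptive purpose of the analysis. A planned effect estimate or comparison by dose would call for a fresh look.

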1)Ability to provide informed consent	Clinical interview
2) Diagnosis of bipolar I disorder, bipolar 2 disorder or	DSM-IV by means of SCID
bipolar disorder NOS and currently meeting criteria for a	
major depressive episode	
3) Depression of sufficient severity to score at least 16 on the	Hamilton Depression Rating
first 17 items of the Hamilton Depression Rating Scale	Scale
including the atypical depression items addendum	
4) Age 18-50 years old	Clinical interview

5) Patients who were on psychiatric medication at	Clinical interview
presentation will have failed that regimen, as defined as not	
achieving at least partial remission after an adequate dose of	
medication for at least six weeks. Benzodiazepines and	
hypnotics are allowed throughout the study	
6) Females of child-bearing potential must be willing to use	Clinical interview
an acceptable method of birth control throughout the study:	
abstinence, birth control pill, male condom, IUD, depo-	
provera, Norplant, male sterilization or female sterlization	
7) Subject is likely to tolerate medication washout if	Clinical interview
indicated	
8) Must be enrolled in IRB#4815	Review of records

Exclusion criteria

Criterion	Method of Assessment
1)Diagnosis of any other major psychiatric disorders such as	As defined by DSM-IV by
schizoaffective disorder, current psychotic depression, or	means of SCID; urine drug
current drug or alcohol abuse (within two months before the	screen
study) or recent drug or alcohol dependence (within six	
months before the study); anorexia nervosa or bulimia	
nervosa within in the last year; Meet DSM-IV criteria for	
manic episode at the time of screening	
2)Previous failed trial of lurasidone, defined by at leastv six	Clinical interview
weeks of treatment at the dose of 20 mg per day or more.	
Experienced intolerable side effects of lurasidone in the past.	
Taking any medications that are contraindicated with	
lurasidone unless there is a plan to stop these as part of the	
washout.	
3)History of clinical deterioration when any of the	Clinical interview
medications that the patient is taking at presentation have	
been discontinued in the past if they will be discontinued as	
part of the washout.	
4)First-degree family history of schizophrenia if the subject	Clinical interview
is less than 33 years old.	
5)Significant active physical illness, including blood	Medical history by a
dyscrasias, lymphomas, hypersplenism, endocrinopathies,	physician, physical exam,

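### The named depression scale switches from HAM-D to MADRS when lurasidone starts, so no same-scale depression change across the start of treatment is assured

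*Combined protocol and SAP*

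**What the plan says.** **Before lurasidone.** The Inclusion Criteria set the severity threshold on the "first 17 items of the Hamilton Depression Rating Scale", with the atypical-depression addendum. Under Medication Washout, "A CGI, HAM-D, YMRS, psychotic symptoms of BPRS and CSSRS will be performed at least weekly". The same section applies a HAM-D threshold again: only patients still above it "at the clinical appointment one week before the scheduled PET scan will continue".

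**During lurasidone.** The Clinical Treatment section states: "At each visit, the study psychiatrist will complete the MADRS, YMRS, CGI, CSSRS, psychotic symptoms of BPRS, and SAFETEE-GI". The HAM-D is not in this list, and the MADRS is named nowhere else in the document. Patients also fill in self-rating forms, which are not named.

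**Scans.** PET Imaging says: "One scan will be before lurasidone is initiated and the second will be four weeks (+/- one week) after starting lurasidone". It names no depression scale at either scan. The safety check within 48 hours of a scan names only the CSSRS.

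**Purpose and analysis.** Medication Washout says: "The design will also allow us to measure the clinical response to lurasidone that is independent from an interaction with the previous medications". The Data Analysis Plan aims at feasibility data and at visualizing all data. It defines no depression outcome, baseline or change score.

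**Visit frequency.** Frequency of Clinical Visits says: "Throughout the study, outpatients will meet with a treating MIND or DES psychiatrist at least once a week in-person". Clinical Treatment makes visits weekly "unless the participant is rated much improved at week four, in which case visits will be biweekly thereafter".

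**The concern.** A change score needs the same instrument before and after. As the two rating lists are written, the HAM-D has pre-treatment values only and the MADRS has on-treatment values only. HAM-D and MADRS totals are different scores, and subtracting one from the other does not give a change in depression.

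The study pairs a pre-drug scan with an on-drug scan to examine how lurasidone acts against depression. The natural companion to a change in PET signal is a change in depression severity over the same interval. In a small pilot that relies on looking at the data, that would be an obvious plot to draw. If staff follow the two lists literally, the MADRS baseline is never taken, and a rating missed before the first dose cannot be recovered later.

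**Working it through.** The protocol gives no figure to reproduce, so the check sets its schedules side by side.

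**Step 1: the two rating lists** (Medication Washout and Clinical Treatment)

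| Rating | Washout | Lurasidone |
|---|---|---|
| CGI | yes | yes |
| YMRS | yes | yes |
| CSSRS | yes | yes |
| BPRS psychotic symptoms | yes | yes |
| HAM-D | yes | not listed |
| MADRS | not listed | yes |
| SAFETEE-GI | not listed | yes |

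Ratings shared: 4 of the 5 in washout. Depression scales stated in both phases: 0 of 2.

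**Step 2: what the treatment-visit sentence can cover**

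- *Treatment visits only.* If the first weekly visit is at week 1 (an assumption), the first MADRS comes about one week after the first dose. MADRS change then starts on drug, and the HAM-D has no on-treatment value.
- *A visit at or before the first dose as well.* A MADRS baseline exists and the change can be computed.

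The first reading is the more natural. The sentence sits in the treatment section, follows the treatment-visit schedule and includes SAFETEE-GI, while washout has its own explicit list. The wording does not settle it.

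**Step 3: depression ratings near scan 1.** Washout HAM-D is at least weekly, and the medication-free three weeks run up to the scan. A HAM-D should therefore fall within about a week of scan 1. The threshold check one week before the scan need not be the last one.

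**Step 4: depression ratings near scan 2.** The permitted window is 4 − 1 = week 3 to 4 + 1 = week 5. Nominal visit weeks are:

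- Weekly rule: 1, 2, 3, 4, 5. A scan at week 3, 4 or 5 coincides with a MADRS visit.
- Biweekly rule after a rating of much improved at week four: 1, 2, 3, 4, 6. A scan at week 3 or 4 coincides with a visit. A scan at week 5 is 5 − 4 = 1 week after the last MADRS.

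The week 6 visit may not be on treatment, since Clinical Treatment ends treatment at up to four weeks or the second scan. It should not be counted on as a substitute.

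The scan 2 gap is therefore one week. It arises only for a week 5 scan, in a patient rated much improved at week four, and only if the biweekly rule prevails over the weekly one.

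**The case against.** The strongest reply is that the document shows only that no pre-dose MADRS is named, not that none is taken. Patients are first assessed under separate screening protocols and IRB#4815, which may include one. The unnamed self-rating forms might include a depression measure. There is no schedule-of-assessments table to rule out a pre-dose visit. This stands as a limit on certainty, but it does not remove the gap: nothing in this document assures a baseline, and the self-rating forms appear only in the treatment section.

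Second, the sentence about measuring clinical response is there to justify the washout. It names no scale and promises no depression change score. The CGI is recorded in both phases and can show global response. This also stands, and it keeps the point modest. But the CGI does not measure depression severity specifically.

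Third, a reader might infer that depression is not rated near either scan. The documents do not support that. Weekly HAM-D falls near scan 1, and a weekly MADRS coincides with scan 2 at weeks 3 and 4. The remaining week 5 gap is no larger than the protocol's own one-week scan tolerance.

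A reader might also infer that a planned analysis cannot be carried out. That is not supported either: the Data Analysis Plan specifies no test, and no section commits to relating depression change to PET change.

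**Conclusion.** The point holds in a limited form. The named depression scale changes at the start of lurasidone, and on the more natural reading no depression scale is recorded both before and during treatment. Confidence is medium, because the conclusion depends on the treatment-visit sentence not extending to a pre-dose visit and on no baseline MADRS being collected under the linked protocols.

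The size can be given only as counts: one of five washout ratings is dropped, it is the depression scale, and neither of the two depression scales is stated in both phases. How much depression change would go unmeasured cannot be computed from the documents. What is lost is descriptive value in a feasibility study. This is a low-cost improvement, not a flaw that invalidates the study.

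The conflict over visit frequency is real but secondary. Its effect on scan 2 is confined to the week 5 case, and the missing baseline does not depend on it.

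**What to change.** 1. Add a MADRS at the last visit before the first lurasidone dose, near PET scan 1, and name it as the baseline for MADRS change. If the treatment-visit list is already meant to cover a pre-dose visit, say so.
2. Repeat the HAM-D, with the same items and addendum as at entry, at the visit nearest PET scan 2. This gives a same-scale change even for patients who have already started lurasidone without a MADRS baseline, provided that visit is still to come.
3. Reconcile the visit-frequency statements in Frequency of Clinical Visits and Clinical Treatment.

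The cost is one or two extra ratings per patient, by psychiatrists already seeing the patient at existing visits, plus a short amendment. It needs no added patients, scans or staff, and the added ratings change no treatment rule. Patients already dosed cannot regain a MADRS baseline, and for those already past scan 2 neither added rating can be taken.
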